### **5.6. Protocol Deviations**

The following sections describe any protocol deviations that relate to the statistical analyses.

It is possible that unexpected deviations will arise, becoming known only after the study has been active for a long period of time; hence more deviations may be added. A full list of protocol deviations for the study report will be compiled prior to database closure. As of this writing, the protocol deviations can all be found in Sections 5.6.1 and 5.6.2 below.

The list of patients along with the excluding protocol deviation will be put into the trial master file.

#### **5.6.1. Deviations Assessed Prior to Randomization**

Granted exceptions to the inclusion or exclusion criteria are not expected to occur. Any patient who enters the study when the inclusion or exclusion criteria would have prevented entry will be considered to have had a protocol deviation.

#### **5.6.2. Deviations Assessed Post-Randomization**

Only protocol deviations that are thought to effect the efficacy of tofacitinib will be considered. Each of the cases will be reviewed by the team and a clinical judgment made in

each particular circumstance as to whether efficacy would have been effected in the cases of these specific classes of protocol deviations assessed post randomization:

- Patients who receive prohibited concomitant medications;
- Patients who interrupt therapy for longer than allowed (less than 80% compliant during the double-blind study treatment period);
- Patients who were randomized but took incorrect treatment;
- Patients whose background RA medications are changed in violation of protocol.

Each patient's presence on the list of exclusion from the per-protocol analysis means that there was at least one deviation for that patient clinically judged to effect efficacy.

## **6. ENDPOINTS AND COVARIATES**

### **6.1. Efficacy Endpoints**

#### **6.1.1. Primary Efficacy Endpoint**

- *Change from Baseline in DAS28-4(CRP) at Week 12.*

#### **6.1.2. Secondary Efficacy Endpoints**

- *Change from Baseline in DAS28-4(ESR) at Week 12.*
- *ACR20, ACR50 and ACR70 response at Week 12.*
- *Remission at Week 12, as assessed by:  $DAS28-4(CRP) < 2.6$  and  $DAS28-4(ESR) < 2.6$ .*
- *LDA at Week 12, as assessed by:  $DAS28-4(CRP) \leq 3.2$  and  $DAS28-4(ESR) \leq 3.2$ .*
- *Change from Baseline in HAQ-DI at Week 12.*
- *HAQ-DI response (decrease of at least 0.22) at Week 12.*
- *Change from Baseline in the SF-36 8 domain scores and 2 component scores at Week 12.*
- *Change from Baseline in the FACIT-Fatigue scale at Week 12.*
- *Change from Baseline in the EQ-5D at Week 12.*

### 6.1.3. Other Efficacy Endpoints

- *Primary and secondary efficacy endpoints at other selected post-baseline scheduled visits.*

### 6.2. Safety Endpoints

- *All adverse events (AEs), including serious adverse events (SAEs).*
- *Clinically significant abnormal laboratory parameters.*

### 6.3. Other Endpoints

None.

### 6.4. Covariates

The baseline values of the efficacy endpoint will be used as covariates when the treatment effect is assessed on the change from baseline for the efficacy endpoints.

## 7. HANDLING OF MISSING VALUES

In general, missing values will not be imputed for descriptive statistics.

For continuous efficacy endpoints, the missing values post-baseline will be handled in a linear mixed-effect model with repeated measures for this continuous variable, where the values are assumed to be missing at random.

In addition, if the DAS28 values post-baseline are missing, method of multiple imputation (MI) will be used to impute any missing DAS28 values. The SAS MI procedure will be used to impute missing DAS28 values for each group. One thousand (1000) complete data sets will be generated and analyzed using the SAS MIANALYZE procedure to combine results from these complete sets.

For binary efficacy endpoints, last observation carried forward (LOCF) mixed components method will be used to impute any missing components in binary composite endpoints before dropout for any reason. Only post-baseline values will be carried forward. Any subject whose response status at any time cannot be determined even after the imputation above will be counted as a non-responder at that time (non-responder imputation, NRI). This includes all visits after dropout for any reason.

Also as a sensitivity check, the “as-is” values of the binary efficacy endpoints will be analyzed. That is, the values of binary composite endpoints will be calculated without applying any imputation to the components.

In addition, missing values for safety endpoints will not be imputed.

## 8. STATISTICAL METHODOLOGY AND STATISTICAL ANALYSES

In general, number and percent will be presented for binary variables, and number, mean, standard deviation, standard error of the mean, minimum, 1st, 2nd and 3rd quartiles and maximum will be presented for continuous variables. In addition, graphics may be used to present the data.

### 8.1. Statistical Methods

#### 8.1.1. Analysis of Longitudinal Continuous Data

*The analysis will be conducted using a linear mixed effect model with repeated measures (MMRM), which will include treatment (tofacitinib MR 11 mg QD and IR 5 mg BID), visit, and treatment by visit interaction as fixed effects. Subjects will be a random effect and unstructured covariance will be assumed for the within-subject errors. If there are convergence problems with this model, sequential structures will be applied until the problems resolved; autoregressive 1 and compound symmetry.*

If there is modeling of actual values, the explanatory variable of visit will include baseline as one of the longitudinal values. When modeling the change from baseline values, the variable of visit will start with the first post-baseline visit, and the actual baseline value will be included as a covariate. At each visit, estimates of mean values, the mean differences between the treatment groups and the associated 2-sided 95% confidence interval (type-I error [alpha] of 0.025 in each tail) will be derived from the model.

#### 8.1.2. Analysis of Non Longitudinal Continuous Data

The same approach as in Section 8.1.1 will be applied, except that the model will not include visit, treatment-by-visit interaction, or patient as a random effect. In this case, the model is an analysis of covariance (ANCOVA) model.

#### 8.1.3. Analysis of Binary Data

The normal approximation for the difference in binomial proportions will be used to estimate the 95% confidence interval.

The normal-approximation to the test statistic for the difference in binomial random variables is calculated as

$$Z_i = \frac{\hat{p}_i - \hat{p}_c}{\sqrt{\frac{\hat{p}_i(1-\hat{p}_i)}{n_i} + \frac{\hat{p}_c(1-\hat{p}_c)}{n_c}}}$$

where  $\hat{p}$  refers to the relative frequency,  $n$  to sample size, the subscript  $c$  refers to a comparator group (i.e., tofacitinib IR 5 mg BID) and the subscript  $i$  refers to a test group (i.e., tofacitinib MR 11 mg QD).

Two-sided 95% confidence intervals are formed by:

$$(\hat{p}_i - \hat{p}_c) \pm 1.96 \sqrt{\frac{\hat{p}_i(1 - \hat{p}_i)}{n_i} + \frac{\hat{p}_c(1 - \hat{p}_c)}{n_c}}$$

In addition, this method will also be used in all secondary analyses involving binary variables.

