### **9.2.5. Analysis of Secondary and Other Efficacy Endpoints**

For each endpoint, treatment comparisons are performed at Week 12 and other time points when assessed. There is no non-inferiority testing in these analyses. The point estimate of the treatment difference and the associated 2-sided 95% confidence intervals (CIs) will be calculated, for descriptive purposes.

All the secondary and other efficacy analyses are based on FAS.

The continuous data, i.e., change from baseline in DAS28-4(ESR) and HAQ-DI will be analyzed in a similar manner as described for change from baseline in DAS28-4(CRP) in the primary analysis.

Dichotomized data will be summarized and compared between two treatment groups using the normal approximation to the difference in proportions. The 2 sided 95% confidence interval of the treatment difference will be constructed. Examples of the secondary and other efficacy endpoints for each scheduled post-baseline measurement are:

- ACR20, ACR50 and ACR70 response.
- Remission, as assessed by: DAS28-4(CRP) < 2.6 and DAS28-4(ESR) < 2.6.
- LDA, as assessed by: DAS28-4(CRP) ≤ 3.2 and DAS28-4(ESR) ≤ 3.2.
- HAQ-DI response (decrease of at least 0.22).

Subjects who drop-out for any reason will be considered as a non-responder (non-responder imputation [NRI]). For the composite endpoint, the last observation carried forward (LOCF) mixed components method will be used to impute any missing components before drop-out. Only post-baseline values will be carried forward in the latter case.

Descriptive statistics of the patient-reported outcome instruments for baseline and for each scheduled post-baseline measurement will be provided.

Remaining secondary and other efficacy analyses will be detailed in the analysis plan.

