### **8.2.2. Analysis of Secondary and Other Efficacy Endpoints**

All analyses of secondary and other efficacy endpoints are based on the FAS.

The change from baseline in longitudinal continuous variables (i.e. DAS28-4(ESR), HAQ-DI, other 6 components of the ACR criteria, the 8 domains and 2 component scores of SF-36) will each be analyzed using the MMRM model as described in Section 8.1.1 and the missing values will not be imputed.

The change from baseline in non-longitudinal continuous variables (i.e. EQ-5D utility score and FACIT fatigue scale) will each be analyzed using ANCOVA model as described in Section 8.1.2 and the missing values will not be imputed.

Binary variables (i.e. the ACR variables [ACR20, ACR50 and ACR70], DAS28 responses [DAS28 ≤3.2, DAS28 <2.6] which include DAS28-4[CRP] and DAS28-4[ESR], and decrease [at least 0.22] in HAQ-DI) will be analyzed using the normal approximation to the difference in response rates, as described in Section 8.1.3. The missing values will be handled according to the approach described in Section 7.

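### Remission, low disease activity and HAQ-DI response are compared without the Day 1 score, which probably costs a little precision in descriptive intervals

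*SAP*

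**What the plan says.** SAP 8.1.3 sets the method: "The normal approximation for the difference in binomial proportions will be used to estimate the 95% confidence interval". Its formula uses only the two observed proportions and the two arm sizes, and the section adds that "this method will also be used in all secondary analyses involving binary variables". SAP 8.2.2 applies it to ACR20/50/70, to the DAS28 thresholds of 2.6 and 3.2 (CRP and ESR versions) and to a HAQ-DI fall of at least 0.22. All of these "will be analyzed using the normal approximation to the difference in response rates".

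Protocol 9.2.5 has the same method: "Dichotomized data will be summarized and compared between two treatment groups using the normal approximation to the difference in proportions". The two documents agree, so this is a deliberate choice and not an inconsistency.

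The covariate rule is in SAP 6.4: "The baseline values of the efficacy endpoint will be used as covariates when the treatment effect is assessed on the change from baseline". Under SAP 8.1.1, 8.2.1 and 8.2.2, the changes in DAS28-4(CRP), DAS28-4(ESR) and HAQ-DI are analysed with the baseline value in the model. The responder versions of the same scores are not.

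On the status of the secondary endpoints, Protocol 9.2.5 says: "There is no non-inferiority testing in these analyses". It adds that the differences and intervals "will be calculated, for descriptive purposes".

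**The concern.** Remission and LDA are absolute cut-points on the Week 12 DAS28, so a subject who starts lower has less far to fall. Baseline DAS28 is therefore a natural predictor of both. HAQ-DI response depends on baseline for another reason. Protocol 4.1 sets no minimum HAQ-DI and admits functional Class I, and a subject who starts below 0.22 cannot fall by 0.22.

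Both scores are measured at the Day 1 visit (Protocol 6.2.1). Protocol 5.1 describes no stratified randomisation, so nothing in the stated design balances them between arms. The secondary objectives concern similarity, with no margin. For these endpoints the reader has only the estimate and its interval, so unused precision makes the display less informative than it could be at almost no cost.

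**Working it through.** **1. The plan's own figures.** The only sizing is for the primary endpoint (Protocol 9.1: margin 0.6, SD 1.3, true difference 0, one-sided alpha 0.025, power 90%).

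- Per arm: 2 × (1.960 + 1.282)² × 1.3² / 0.6² = 98.7, so 99 (stated 100).
- Power at 100 per arm: Φ(0.6 / (1.3 × √(2/100)) − 1.96) = Φ(1.304) = 90.4% (stated 90%).
- Half-width: 1.96 × 1.3 × √(2/100) = 0.360 (stated 0.36).

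All three reproduce, and the present point does not touch them. No precision is stated for any responder endpoint.

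**2. Crude responder interval at 100 per arm.** The SAP 8.1.3 formula with equal rates p gives a half-width of 1.96 × √(2p(1−p)/100):

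- p = 0.2: 11.1 points
- p = 0.3: 12.7 points
- p = 0.5: 13.9 points

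**3. What adjustment can save.** If baseline explains a fraction R² of the variance of the binary outcome, the adjusted half-width is about √(1−R²) times the crude one. The documents give neither R² nor a correlation, so a range is needed. With a normal latent outcome at p = 0.5, a correlation of 0.3 gives R² = 0.057 (2.9% narrower) and 0.5 gives R² = 0.161 (8.4% narrower).

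This was checked by simulating a standardised logistic risk difference against the crude one: 3,000 trials per setting, 100 per arm, no true difference. Mean half-widths are in percentage points:

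| Correlation | p = 0.3 crude → adjusted | p = 0.5 crude → adjusted | Trials with adjusted interval wider |
|---|---|---|---|
| 0 | 12.63 → 12.70 | 13.79 → 13.86 | 91% |
| 0.1 | 12.62 → 12.65 | 13.79 → 13.82 | 73-75% |
| 0.2 | 12.63 → 12.55 | 13.79 → 13.68 | 30-34% |
| 0.3 | 12.63 → 12.36 | 13.79 → 13.46 | 3-6% |
| 0.5 | 12.63 → 11.70 | 13.79 → 12.70 | almost none |

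The saving is about 0.3 points at 0.3 and 0.9 to 1.1 points at 0.5. At zero the cost is about 0.5% of width. Coverage was 93.8-95.7% for the crude interval and 94.2-95.5% for the adjusted one.

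**4. On the DAS28 scale.** The protocol's SD of 1.3 is used for the change. Assumed, because the documents do not give them: baseline mean 5.5, baseline SD 1.0, Week 12 mean 3.4. With c the correlation between baseline and change, the Week 12 SD is √(1 + 1.69 + 2.6c) and the baseline/Week 12 correlation is (1 + 1.3c) divided by that SD. For c = −0.7, −0.5, −0.3 and −0.2 the correlation is 0.10, 0.30, 0.44 and 0.50. The implied rates are Φ((2.6 − 3.4)/SD), about 20-29%, for remission and Φ((3.2 − 3.4)/SD), about 42-45%, for LDA.

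| Baseline/Week 12 correlation | Adjusted/crude SE, remission and LDA |
|---|---|
| 0.10 | about 1.00 |
| 0.30 | 0.97-0.98 |
| 0.44 | 0.94-0.95 |
| 0.50 | 0.91-0.93 |

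Counting an assumed 10% of subjects as dropouts and therefore non-responders (the SAP 7 rule) made the gain slightly smaller. Adjusted coverage stayed at 94-96%. HAQ-DI response was not simulated, and no size is claimed for it.

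**The case against.** The strongest reply is that nothing is broken. The crude difference is transparent, needs no model and has close to nominal coverage. Protocol 9.2.5 attaches no margin or test to these intervals. SAP 8.2.1.1 rests the non-inferiority conclusion on the primary analysis alone, which already adjusts for baseline. All of this stands, and it limits how much weight the point can carry.

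Four stronger readings are tempting, and the documents do not support them.

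- *Every responder interval is wider than it needs to be.* This depends on an association that the documents do not report. At a correlation of 0.1 or less the adjusted interval is usually the wider one, though by very little. ACR20/50/70 are relative improvements across several components with no single baseline score, and no gain has been shown for them.
- *Similarity is judged only from these intervals.* Secondary objective 1 also names the DAS28-4(ESR) change, and objective 2 is defined by HAQ-DI change. Both have baseline-adjusted analyses.
- *Chance imbalance at baseline biases the crude comparison.* An imbalance does shift the estimate in a given trial, but the width of the crude interval already allows for it. This is the precision point in another form.
- *Dropout removes the gain.* With 10% counted as non-responders the gain was slightly smaller, but it remained.

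**Conclusion.** The point holds as a modest, optional gain in precision for remission, LDA and HAQ-DI response. It is not an error in the plan and has no bearing on the non-inferiority conclusion.

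For remission and LDA the standard error would be about 0% smaller at a baseline/Week 12 correlation of 0.1, 2-3% at 0.3, 5-6% at 0.44 and 7-9% at 0.5, and slightly less with dropouts counted as non-responders. These figures rest on the assumed baseline and Week 12 values and on a correlation that only trial data could supply. For HAQ-DI response the argument is structural and its size is unknown.

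The balance still favours adjustment. The possible loss is about 0.5% of width, the possible gain is several times that, and the risk-difference scale is unchanged.

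**What to change.** Before unblinding, add to SAP 8.1.3, for remission, LDA and HAQ-DI response only:

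- The MR minus IR risk difference is estimated from a logistic model with treatment and the matching baseline score: DAS28-4(CRP), DAS28-4(ESR) or HAQ-DI.
- It is standardised over the FAS (g-computation), with a delta-method or bootstrap 95% interval. Which of the two is used should be named in advance.
- The missing-response rules of SAP 7 apply unchanged.
- The crude rates and crude difference are reported alongside, and serve as the fallback if the model does not fit.

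SAP 6.4 needs a matching sentence. ACR20/50/70 stay on the crude method. Protocol section 9 lets the SAP modify the planned analyses and requires a protocol amendment only for major changes to the primary endpoint or its analysis, so a SAP amendment should be enough.

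The cost is a paragraph, a short macro and a negligible loss of precision if baseline turns out not to be prognostic. Added after unblinding, the same analysis could look data-driven.

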## **8.2. Statistical Analyses**

### **8.2.1. Analysis of Primary Efficacy Endpoints**

The primary endpoint DAS28-4(CRP) change from baseline will be analyzed using MMRM described in Section 8.1.1 on the FAS. The patient is required to have a baseline and at least one non-missing on-study assessment of DAS28-4(CRP) to be included in the analysis. Missing values will not be imputed.

Non-inferiority of tofacitinib MR 11 mg QD to IR 5 mg BID will be concluded if the upper bound of the 2-sided 95% confidence interval of differences between the treatment groups (MR 11 mg QD – IR 5 mg BID) at Week 12 is less than the pre-specified non-inferiority margin of 0.6.

#### **8.2.1.1. Sensitivity/Robustness Analyses**

To support the interpretation of the primary analyses, some robustness or sensitivity analyses will be performed for the primary endpoint. However, the conclusions (non-inferiority) for comparison of the primary endpoint between tofacitinib MR 11 mg QD and IR 5 mg BID group is purely based on results of the primary analysis.

One of the robustness analyses is ‘Per Protocol’ analysis, that is, the same primary analysis for the primary endpoint will be conducted using PPAS rather than the FAS.

Other robustness analyses will be performed using the FAS as follows:

- MMRM model described in Section 8.1.1 with compound symmetry instead of unstructured covariance. Missing values will not be imputed.
- MMRM model described in Section 8.1.1 with unstructured covariance. Missing values will be imputed using the method of MI as described in Section 7.
- ANCOVA model described in Section 8.1.2 at Week 12. Missing values will not be imputed.

#### **8.2.1.2. Subset Analysis**

For DAS28-4(CRP) change from baseline, subgroup analysis will be performed by following subsets at baseline/screening:

- Sex (Male, Female),
- Body weight (<55 kg, ≥55 kg),
- Age (<65 years old, ≥65 years old),
- Rheumatoid factor at screening (Negative, Positive),
- Disease duration (<5 years, ≥5 years),
- Methotrexate dose at baseline (≤8 mg/week, >8 mg/week) and
- DAS28-4(CRP) at baseline (≤5.1, >5.1).

### **8.2.2. Analysis of Secondary and Other Efficacy Endpoints**

All analyses of secondary and other efficacy endpoints are based on the FAS.

The change from baseline in longitudinal continuous variables (i.e. DAS28-4(ESR), HAQ-DI, other 6 components of the ACR criteria, the 8 domains and 2 component scores of SF-36) will each be analyzed using the MMRM model as described in Section 8.1.1 and the missing values will not be imputed.

The change from baseline in non-longitudinal continuous variables (i.e. EQ-5D utility score and FACIT fatigue scale) will each be analyzed using ANCOVA model as described in Section 8.1.2 and the missing values will not be imputed.

Binary variables (i.e. the ACR variables [ACR20, ACR50 and ACR70], DAS28 responses [DAS28 ≤3.2, DAS28 <2.6] which include DAS28-4[CRP] and DAS28-4[ESR], and decrease [at least 0.22] in HAQ-DI) will be analyzed using the normal approximation to the difference in response rates, as described in Section 8.1.3. The missing values will be handled according to the approach described in Section 7.

### **8.2.3. Analysis of Safety Data**

*The safety analysis will be conducted on the safety analysis set.*

The Sponsor has standard (i.e., used for all its clinical trials) summary displays and listings for MedDRA-coded adverse events, demography, medical history, length of time in study and discontinuation, concomitant and concurrent medications, physical examination, ECG, laboratory tests, weight, pulse rate, and blood pressure. These standards, called Pfizer Data Standards, will be utilized in the reporting of these routine safety variables (Pfizer Data Standards Rulebook).

### 8.2.3.1. Adverse Events

Adverse events will be listed and summarized within treatment group in accordance with the Pfizer Data Standards. Adverse events, serious adverse events and discontinuation due to adverse event will also be summarized by subsets described in Section [8.2.1.2](#).

Adverse events met following the Standardised MedDRA Queries (SMQs) will be summarized within treatment group.

- Hypertension
- Congestive Heart Failure
- Dyslipidaemia
- Erythropenia
- Leukopenia
- Acute Renal Failure
- Ischemic Heart Disease
- Ischemic Cerebrovascular Disease
- Myocardial Infarction
- Possible Drug-Related Hepatic Disorders

Serious infection events and treated infection events will be summarized per visit, respectively.

Herpes zoster events defined by MedDRA Preferred Terms in [Appendix 4](#) will be summarized within treatment group.

Adverse events reviewed in the following adjudication/review committees will be listed.

- Cardiovascular safety endpoints adjudicated by the Cardiovascular Endpoint Adjudication Committee (CV-EAC).
- Malignancies adjudicated by Malignancy Adjudication Committee (MAC)
- Opportunistic infections reviewed by the Opportunistic Infection Review Committee (OIRC).
- Hepatic events reviewed by the Hepatic Event Review Committee (HERC).

- Gastrointestinal perforation events reviewed by Gastrointestinal Perforation Review Committee (GIPRC).
- Interstitial lung disease (ILD) events reviewed by the Interstitial Lung Disease Review Committee (ILDRC).
- Potentially malignant tumors, suspicious lymphadenopathy, possible extranodal lymphoproliferative disorder (LPD) reviewed by the central pathologists.

